6.10.4 Additional Summaries

Key efficacy endpoints for patients in the FAS in Part 1 and Part 2 will be listed by individual patient alongside a summary (Mean (SD)) by treatment group and by indication group (Part 2 only: AKC/VKC and SAC/PAC) at each timepoint. Details of endpoints to be presented are as follows:

- Comfort score:
 - Total and average daily score will be presented for each treatment period.
- Visual Acuity:
 - Number of ETDRS letters will be presented for right eye, left eye and the score from worse of the two eyes for each visit.
- Clinical scores:
 - The total clinical score, the overall symptom and sign subcomponent scores will be presented for each visit.
- Tear film break up time:
 - TBUT in seconds will be presented at each visit.

6.11 Pharmacokinetics

Serum concentrations of nomacopan will be listed and summarised over time. If < 50% of patients have data which are greater than LLOQ then table outputs with summary statistics will not be produced. Should the summary statistics be produced values below the lower limit of quantification (LLOQ) will be set to $0.5 \times LLOQ$ for calculation of summary serum concentration statistics.

6.12 Pharmacodynamics

Serum terminal complement activity measured by CH50 U Eq/ml and change from baseline will be summarised by treatment group for each visit.

Summary statistics will include observed values, change from baseline and the ratio to baseline (% activity). Ratio will be calculated as:

$$Ratio \ to \ baseline = \frac{Observed \ value}{Baseline \ value} * 100$$

Given the very small amount of nomacopan being administered topically, the expectation is that active and placebo patients in Part 2 will have equivalent CH50 values and a comparison between the groups will be tabulated.

All pharmacodynamic data will be listed.

6.13 Anti-drug Antibodies

. All anti-drug antibody data will be listed.

6.14 Safety Evaluation

6.14.1 Adverse Events

AEs will be coded using the latest MedDRA dictionary version. The version used will be indicated in the data summaries and listings.

Ocular AEs will be identified using SOC "Eye disorders".

A treatment-emergent adverse event (TEAE) is defined as an AE that started on or after the start of the administration of study treatment. If AE dates are incomplete and it is not clear whether the AE was treatment-emergent, it will be assumed to be treatment-emergent. When the AE occurs on the same day as start of administration of study treatment a separate file will be transferred from data management to indicate whether they are treatment emergent or not (see Data Management Plan section 6).

If it is not confirmed via Data Management, the start date will be imputed as the date of the first dose of study drug. AEs will be considered treatment-emergent if all or part of the date of onset of the AE is missing and it cannot be determined if the AE meets the definition for treatment-emergent.

Any AE commencing after the last administration of study treatment (Day 56) plus 30 days will not be considered treatment emergent.

A treatment-related TEAE is defined as a TEAE that is possibly related or related to the study treatment. If the TEAE has a missing relationship it is assumed to be related to the study treatment for analysis purposes.

6.14.1.1 **Primary Endpoint**

The number and percentage of patients who experienced ocular TEAEs will be presented for each treatment group. Treatment groups will be presented in the following order: "Part 1, Treatment: nomacopan 0.25% eye drops", "Part 2, Treatment: nomacopan 0.25% eye drops", "Part 2, Treatment: Placebo".

The difference in the percentage of patients (nomacopan -placebo) and exact 95% confidence interval for the difference, using Chan and Zhang method (1999), will be presented for those in part 2 of the study (nomacopan-placebo) and for those in both parts of the study combined (nomacopan-placebo).

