8.1.5 Suspected Unexpected Serious Adverse Reaction (SUSAR)

A serious adverse reaction, the nature or severity of which is not consistent with the applicable product information (e.g. IB for an unapproved investigational product or Summary of Product Characteristics for an approved product).

Treatment Emergent Adverse Events (TEAEs)

Treatment emergent adverse events (TEAEs) are undesirable events not present prior to medical treatment, or an already present event that worsens either in intensity or frequency following the treatment.

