8.2 Procedures for Recording of Safety Events

8.2.1 General

All adverse events occurring during the Study (from the time point of signing of the ICF until completion of patient's study participation or premature withdrawal) observed by the

investigator or reported by the patient, whether or not attributed to the IMP, shall be recorded in patient's medical records and on the eCRF.

The following information shall be recorded:

- Description
- Date of onset and end date
- Severity
- Assessment of relatedness to the IMP
- Seriousness
- Measures taken for management of the AE
- Outcome of the event

Follow-up information should be provided as necessary.

AEs considered as being related to the IMP as judged by a medically qualified Investigator, or the Sponsor, must be followed until their resolution or when patient's status is considered as stable. All related AEs that result in a patient's withdrawal from the Study or are present at the end of the Study, should be re-evaluated and if needed followed until a satisfactory resolution occurs.

It will be left to the investigator's clinical judgment whether or not an AE is of sufficient severity to require termination of IMP administration. A patient may also voluntarily withdraw from IMP administration due to AEs perceived as intolerable. If either of these occurs, the patient will be given appropriate care under medical supervision until symptoms cease or the condition becomes stable.

The severity of reported events shall be assessed on the following scale:

- 1 = mild
- 2 = moderate
- 3 =severe

The causal relationship of AEs to the IMP must be assessed by the investigator, or by a medically qualified designee, in accordance with the following criteria:

| TERM | DEFINITION |
|------------------|---|
| Unrelated | Clinical event with an incompatible time relationship to administration of the investigational medical product (IMP), and that could be explained by underlying disease or other drugs or chemicals or is incontrovertibly not related to the IMP |
| Possibly related | Clinical event with a reasonable time relationship to IMP administration, and that is unlikely to be attributed to concurrent disease or other drugs or chemicals |
| Related | Clinical event with plausible time relationship to IMP administration and that cannot be explained by concurrent disease or other drugs or chemicals |

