11.2 Primary Analysis

Ocular adverse events which have occurred during the 56 days of treatment following randomisation will be considered in the analysis of the primary safety outcome. The difference between the two treatments in the proportion of patients experiencing any ocular treatment emergent AEs as coded under MedDRA System Organ class: Eye disorders will be reported with its associated 95% Confidence interval.

A treatment-emergent adverse event (TEAE) will defined as an adverse event that started, or increased in severity, after the first dose of study medication was taken. The incidence of TEAEs will be summarized by System Organ Class, Higher Level Term and Preferred Term. Additional summaries will be produced, such as summary of serious TEAEs, summary of TEAEs by intensity/severity, or by relationship to study drug.

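### SAP 6.14.1 defines a treatment-emergent event by start date alone and drops the protocol's worsening limb without declaring it, so an ocular AE that begins between consent and first dose and worsens under the same record is left out of the primary endpoint

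*SAP*

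**What the plan says.** The primary endpoint is the incidence of ocular TEAEs in the treatment period. Protocol 11.2 specifies the comparison: "The difference between the two treatments in the proportion of patients experiencing any ocular treatment emergent AEs as coded under MedDRA System Organ class". The class it names is the one for disorders of the eye, and the difference is given a 95% confidence interval. SAP 6.14.1.1 implements it: "The number and percentage of patients who experienced ocular TEAEs will be presented for each treatment group", with an exact Chan and Zhang interval for the difference.

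Three places define the event being counted:

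- **Protocol 11.2:** "an adverse event that started, or increased in severity, after the first dose of study medication was taken".
- **Protocol, TEAE paragraph under 8.1.5:** an event absent before treatment, "or an already present event that worsens either in intensity or frequency following the treatment".
- **SAP 6.14.1:** "A treatment-emergent adverse event (TEAE) is defined as an AE that started on or after the start of the administration of study treatment".

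Protocol 8.2.1 sets the AE recording period: "from the time point of signing of the ICF until completion of patient's study participation or premature withdrawal". Protocol 8.2.2 says that a condition present at screening is recorded as an AE if its frequency, intensity or character worsens during the study. It does not say which onset date the record should carry.

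SAP 6.17 lists three departures from the protocol: the baseline definition, the comfort-score interval and the composition of the safety set. The TEAE definition is not among them.

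**The concern.** Both protocol definitions have two limbs, onset and worsening. The SAP keeps only onset. Its analysis will be the one programmed, so the primary safety endpoint would be computed on a narrower event than the protocol defines, with no reason given. The SAP says that it is based on Protocol Version 8.0, so a version difference does not explain the gap.

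Worsening is a realistic form of local reaction in this trial. Patients must enter with a composite score of at least 18 of 33 (AKC/VKC) or 15 of 27 (SAC/PAC), so their eyes are already symptomatic. With at most 16 randomised patients, one patient's classification visibly changes the reported rate.

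**Working it through.** The documents give no event rate, effect size or power for this endpoint, so there is no planned figure to reproduce. The check compares the definitions and then sets a scale.

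**Step 1. Does another SAP rule restore worsening?** The remaining emergence rules in SAP 6.14.1 cover incomplete dates, onset on the day of first dose, imputation of a start date, and a cut-off at last dose plus 30 days. All of them work on the onset date. The tables in SAP 6.14.1.2 use the same TEAEs. The AE listing carries an emergence flag that would follow the same rule. Nothing restores worsening.

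**Step 2. Can an AE start before the first dose?** Yes. AEs are recorded from signature of the consent form, which the Schedule of Events places at screening. Protocol 6.7 puts entry at 7 ± 2 days after screening, so the longest planned interval is 7 + 2 = 9 days. The Schedule of Events also asks for 4 days between randomisation and first dose.

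**Step 3. Which events are lost?**

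| Ocular event | Protocol 11.2 | SAP 6.14.1 |
|---|---|---|
| Starts after first dose | counted | counted |
| Starts between consent and first dose, worsens on treatment, same record | counted | not counted |
| As above, but the worsening is entered as a new record | counted | counted |
| Present at screening, worsens on treatment, AE dated at the worsening | counted | counted |
| Present at screening, worsens on treatment, AE dated at original onset | counted | not counted |

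Row 2 is a definite loss. Row 5 depends on a dating convention that the documents do not state.

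**Step 4. Size per patient.** I take 16 patients allocated 1:1 as 8 per arm. One patient moves an arm's rate by 1/8 = 12.5 percentage points. SAP 6.14.1.1 also gives a comparison combining both parts. There the nomacopan denominator would be 8 + 3 = 11, and one patient is 1/11 = 9.1 points. A patient is lost only if no other ocular TEAE keeps them in the count.

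**Step 5. Illustration with assumed counts.** Start from an SAP count of 2/8 in each arm. Intervals are exact 95% limits of the Chan and Zhang type, found by inverting two one-sided exact score tests at 0.025 on a 0.01 grid.

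| Worsening-only patients restored | Nomacopan vs placebo | Difference (points) | 95% CI (points) |
|---|---|---|---|
| none | 2/8 vs 2/8 | 0 | about −45 to +45 |
| 1 nomacopan | 3/8 vs 2/8 | +12.5 | about −35 to +57 |
| 2 nomacopan | 4/8 vs 2/8 | +25 | about −25 to +67 |
| 1 placebo | 2/8 vs 3/8 | −12.5 | about −57 to +35 (mirror image) |
| 1 in each arm | 3/8 vs 3/8 | 0 | not computed |

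**Step 6. Chance that anyone is affected.** Let q be the probability that a patient's only qualifying ocular event is a pre-dose event that worsens. The chance of at least one such patient among 16 is 1 − (1 − q)^16. For assumed q of 2%, 5%, 10% and 20% this gives 28%, 56%, 82% and 97%. The documents supply no value for q. Because the definite loss is narrow (row 2), the upper values would need row 5 to be common.

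**The case against.** The strongest reply is that most worsening in this trial does not pass through the gap. Symptoms that patients bring to screening are pre-existing conditions under Protocol 8.2.2, and an AE exists only once they worsen. The natural onset date is then the date of worsening, which is after dosing, and the SAP counts it. A reader might infer that the SAP excludes all aggravation of entry symptoms. The documents do not support that, because it would require sites to enter the original onset date and nothing instructs them to. This part of the objection stands and confines the definite loss to row 2.

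A second reply concerns recording. Protocol 8.2.1 asks for onset date, end date and severity for each AE, with no date of severity change. The simplest way to capture worsening is a new record, which the SAP's rule would count. That is possible, but no such instruction appears in the documents, and the primary count should not rest on an unwritten convention.

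A reader might also infer that the rule makes the drops look better tolerated than they are. That does not follow. The rule applies equally to both arms of a double-masked comparison, and placebo patients with active disease can worsen too. The difference tilts towards nomacopan only if worsening-only patients are more frequent on nomacopan, and the documents give no information on that.

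Finally, Protocol 11.5 says that the study is not powered for the primary analysis, the result is an interval with no pass or fail threshold, and all AEs are listed in full. The intervals in Step 5 overlap heavily, and an omitted event would remain visible in the listing. This limits the damage, but it does not justify an undeclared change to the definition of the primary event.

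**Conclusion.** The discrepancy is established from the text: SAP 6.14.1 narrows the event behind the primary endpoint, no other SAP rule compensates, and 6.17 is silent. The definite consequence is limited to an ocular AE that starts between consent and first dose (at most about 9 days, taking consent at screening), worsens on treatment under the same record, and occurs in a patient with no other ocular TEAE. Worsened screening conditions join it only if they carry their original onset date.

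Each patient lost lowers an arm's rate by 12.5 points, assuming 8 per arm. How many patients are affected, and in which arm, cannot be determined from the documents, so no direction of bias should be claimed. The correction is small and should be made before unmasking, since changing the primary event definition afterwards would look data-driven.

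**What to change.** Before unmasking:

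1. **SAP 6.14.1.** Define a TEAE as an AE with onset, or with an increase in severity, on or after the first administration. First reconcile Protocol 11.2, which mentions severity only, with the paragraph under 8.1.5, which has intensity or frequency, and use one wording in both documents.
2. **Recording rule.** State that worsening of a pre-dose AE, or of a condition present at screening, is entered as a new AE record with the date of worsening as its start date. Restoring the wording alone is not enough, because the AE items listed in Protocol 8.2.1 include no date of severity change from which to program it.
3. **SAP 6.14.1.1.** State that these records count in the primary endpoint when they code to Eye disorders.

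If the onset-only definition is intended, declare and justify it in SAP 6.17 instead.

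The cost is a few sentences in the SAP, a line in the CRF completion instructions, and a check of pre-dose ocular AE records already entered. The reported ocular TEAE rate may rise slightly.

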5.2 Endpoints

5.2.1 Primary endpoint

• Incidence of ocular treatment emergent adverse events during the treatment period (adverse events which have occurred during the 56 days following randomisation (Part 2 of the study only) will be considered in the analysis of the primary safety outcome).

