2.2 Study Endpoints

The primary endpoint of the study is:

• Incidence of ocular treatment emergent adverse events during the treatment period. The adverse events (AEs) which have occurred during the 56 days following randomisation (Part 2 of the study only) will be considered in the analysis of the primary safety outcome.

The secondary endpoints are:

- Post-instillation comfort, as graded on patient diary cards at the following intervals: Days 1 to 14, 15 to 28, 29 to 42 and 43 to 56
- Visual acuity by Early Treatment Diabetic Retinopathy Study (ETDRS) charts comparison from Day 1 to Day 56
- Change from Day 1 in composite clinical scores (including Symptom and Sign subcomponents) at Day 14, 28, 42 and 56

- Number and percentage of patients with Matrix metalloprotease 9 (MMP-9) < 40 ng/mL and ≥ 40 ng/mL assessed using Inflamma Dry (Quidel) device at Days 1, 28 and 56
- Change from Day 1 in Tear film break up time (TBUT) at Day 14, 28, 42 and 56

The exploratory endpoints are:

- Systemic absorption by blood sampling
- If enough tear fluid can be collected analysis of complement C3, C5 and leukotriene B4 (LTB4) will be performed
- A comparison of the number of patients requiring rescue therapy at any stage of the trial and the number on such therapy at the end of the trial

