6.10 Efficacy Evaluation

6.10.1 Primary Endpoint

The primary endpoint is a safety outcome and is described under section 6.14.1.1.

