6.10.3.3 Rescue therapy

The number and percentage of patients that received a rescue medication (as indicated on the Concomitant Medications CRF page) at any stage of the trial (during Day 1 to Day 56 (last dose) and during Day 56 to Day 84 (follow-up visit) to be presented separately) and the number and percentage of patients that were receiving a rescue medication at the end of the trial (indicated as ongoing on the CRF) will be presented in a summary table by treatment group.

The number and percentage of patients that received a rescue medication will be presented for each treatment group for Days 1 to 14, Days 15 to 28, Days 29 to 42 and Days 43 to 56 to compliment the intervals for the efficacy analysis. The percentage will be out of the number of patients at each timepoint who had data for comfort scores to be calculated.

A patient is considered to have taken rescue medication during an interval where the start date (Day 1 or later) occurs during that interval, or if they continue to receive rescue medication that started in a previous interval.

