6.14.1.2 Other Summary Tables

A summary table will present the following for Part 1 and Part 2,:

- TEAEs (events and patients).
- Serious TEAEs (events and patients).
- Serious study treatment related TEAEs (events and patients).
- TEAEs by severity (mild/moderate/severe) (events and patients).
- TEAEs by relationship to study treatment and the pooled study treatment related category (events and patients).
- TEAEs leading to discontinuation of study treatment (patients only).
- Study treatment related TEAEs leading to discontinuation of study treatment (patients only).
- TEAEs leading to death (patients only).

In the above summaries, if a patient experienced more than one TEAE, the patient will be counted once using the most related event for the "by relationship to study treatment" and "related to study treatment" summaries and at the worst severity for the "by severity" summary.

The following tables will be presented:

- TEAEs by system Organ Class (SOC) and Preferred Term (PT).
- TEAEs by PT.
- TEAEs by SOC, PT and severity
- TEAEs by SOC, PT and relationship to study treatment and the pooled related categories (related).

For all of the above, SOC and PT will be presented in decreasing frequency of the total number of patients with TEAEs.

Further details of the above four tables are given below:

- 1. If a patient experienced more than one TEAE, the patient will be counted once for each SOC and once for each PT.
- 2. If a patient experienced more than one TEAE, the patient will be counted once for each PT.
- 3. If a patient experienced more than one TEAE, the patient will be counted once for each SOC and once for each PT at the worst severity.
- 4. If a patient experienced more than one TEAE, the patient will be counted once for each SOC and once for each PT using the most related event.

AE data will be listed in full and this will also include a treatment emergent flag, cessation of event relative to first dosing of study treatment and duration of AE. The listing will be reported by events during "Days 1-56" (treatment period) and "Days 57-84" (follow-up period).

This listing will be repeated presenting only serious TEAEs.

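### SAP 6.14.1.1 does not carry the 56-day limit of the primary endpoint, so ocular events from off-drug follow-up can, but need not, enter the primary comparison

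*SAP*

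**What the plan says.** Three places limit the primary endpoint in time:

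- Protocol 5.2.1 defines it as "Incidence of ocular treatment emergent adverse events during the treatment period".
- Protocol 11.2: "Ocular adverse events which have occurred during the 56 days of treatment following randomisation will be considered in the analysis" of the primary safety outcome.
- SAP 2.2 restates the endpoint and adds that adverse events "which have occurred during the 56 days following randomisation (Part 2 of the study only) will be considered in the analysis" of that outcome.

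The analysis itself is specified elsewhere. SAP 6.10.1: "The primary endpoint is a safety outcome and is described under section 6.14.1.1". That section says: "The number and percentage of patients who experienced ocular TEAEs will be presented for each treatment group". It then asks for the difference in percentages with an exact 95% confidence interval (Chan and Zhang), for Part 2 and for both parts combined. It names no day limit. The term TEAE is defined just above it, in 6.14.1, as an event starting on or after first administration, with this upper bound: "Any AE commencing after the last administration of study treatment (Day 56) plus 30 days will not be considered treatment emergent".

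SAP 6.17 lists three changes from the protocol: the baseline definition, the comfort-score period and the Safety Analysis Set. The window of the primary endpoint is not among them.

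In two other places the SAP does separate treatment from follow-up. Rescue medication (6.10.3.3) is summarised "during Day 1 to Day 56 (last dose) and during Day 56 to Day 84 (follow-up visit) to be presented separately". The adverse event listing in 6.14.1.2 is divided into Days 1 to 56 and Days 57 to 84.

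**The concern.** A programmer who starts from 6.10.1, goes to 6.14.1.1 and applies the TEAE flag from 6.14.1 will count ocular events that start up to 30 days after the last dose. Such events will be on file. Protocol 8.2.1 collects adverse events until the patient's participation ends, and protocol 6.7 brings the patient back about 28 days after dosing. By then patients have returned to usual care (protocol 6.2), so these events belong to a different exposure from the one the endpoint names.

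A programmer who starts from SAP 2.2 will stop the count earlier. Taken literally, that section stops it too early, because its 56 days run from randomisation and not from first dose.

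Two careful people could therefore report different counts for the trial's only primary endpoint, and with about 8 patients per arm a single patient is visible in the result.

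**Working it through.** The documents give no ocular event rate, effect size or power for this endpoint, and protocol 11.4 sets the sample size on practical grounds. There is no planned figure to reproduce, and no event rate is assumed below.

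**Inputs**

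- End of dosing: Day 56 (protocol 17.3).
- Follow-up visit: Day 84 (protocol 17.3).
- TEAE upper limit: last administration plus 30 days (SAP 6.14.1).
- Part 2 size: up to 16, randomised 1:1 (SAP 3 and 4), so 8 per arm if all 16 are enrolled and the arms are balanced.
- Gap between randomisation and first dose: 4 days to be allowed (protocol 17.3, footnote 6).

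**1. Off-drug days counted if 6.14.1.1 is followed as written**

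TEAE limit: 56 + 30 = Day 86. The nominal last visit, Day 84, falls inside it.

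Off-drug days = min(84, 86) − 56 = 28. Share of counted days = 28/84 = 33.3%.

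The exact number for a patient depends on when the follow-up visit takes place. Protocol 6.7 and 17.3 allow ±7 days and the synopsis ±2. With the last dose on Day 56, the earliest visit gives 77 − 56 = 21 days or 82 − 56 = 26 days. The latest gives 86 − 56 = 30 days under either window, because the TEAE limit stops the count there. The nominal 28 of 84 is the figure to quote.

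**2. Effect of one patient on the Part 2 difference**

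1/8 = 12.5 percentage points. This applies to a patient whose only ocular TEAE starts in follow-up; a patient who already had one on treatment changes nothing.

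The table shows the effect with hypothetical counts and an exact 95% interval from inverting two one-sided exact unconditional score tests at 0.025 each.

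| Active v placebo | Difference (points) | Exact 95% CI |
|---|---|---|
| 4/8 v 2/8 | +25.0 | −25.9 to 67.7 |
| 5/8 v 2/8 (one more on active) | +37.5 | −17.3 to 77.9 |
| 4/8 v 3/8 (one more on placebo) | +12.5 | −40.2 to 60.4 |

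The shift can go either way. Its size and direction in the trial cannot be predicted from the documents.

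**3. Where the 56 days end if counted from randomisation**

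If first dose (study Day 1) comes L days after randomisation, day 56 after randomisation is study day 56 − L + 1 = 57 − L. With L = 4 this is study Day 53, so dosing Days 54 to 56 would fall outside the window. A longer gap ends it earlier.

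**4. The two literal readings side by side**

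SAP 2.2 stops at about Day 53. SAP 6.14.1.1 runs to the Day 84 visit. They differ by 84 − 53 = 31 days, and neither ends at Day 56, the end of the treatment period that protocol 5.2.1 names.

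**The case against.** The strongest reply is that the limit is already in the SAP. Section 2.2 does more than name the endpoint: it says which events enter the analysis of the primary safety outcome. On that reading, 6.14.1 defines the TEAE set for all safety tables, 2.2 filters it for the primary table, and the two rules coexist. The 6.14.1.2 listing labels Days 1 to 56 as the treatment period, so a reader could rebuild the intended count from it. The table shells are a separate document (SAP 1) and may state the limit.

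This stands in part. A reader might infer that follow-up events will be counted, or that the endpoint was deliberately widened. The documents support neither: 2.2 still states the narrower rule, and 6.17 declares no change. What remains is that the section named for the primary analysis does not state the limit, although the SAP writes the split out for rescue therapy and the listing. Reading 2.2 as the filter also brings in its count from randomisation, which needs correcting in any case. Protocol 11.2, which speaks of days of treatment, points to the intended anchor.

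The reply is also right about consequence. A reader might infer that one follow-up event could turn the primary result from negative to positive. The plan does not support that. Protocol 11.5 says the study is not powered for the primary analysis, and neither protocol 11.2 nor SAP 6.14.1.1 sets a test or decision rule for it. Whether an interval excludes zero has no role here.

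**Conclusion.** The point holds as a conflict of wording within the SAP, and it should be fixed before unmasking. Section 6.14.1.1 does not carry the treatment-period limit set in SAP 2.2 and protocol 5.2.1 and 11.2, so off-drug ocular events can, but need not, enter the primary comparison.

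If 6.14.1.1 is followed literally, a third of the counted days on the nominal schedule are off drug, and each patient added by follow-up alone moves the Part 2 difference by 12.5 points. These figures assume a last dose on Day 56, a follow-up visit on Day 84 and 8 patients per arm. The randomisation anchor in SAP 2.2 errs the other way, by about 3 dosing days if the gap to first dose is 4 days.

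The effect is confined to the reported estimate and its confidence interval.

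**What to change.** - **SAP 6.14.1.1:** restrict the primary Part 2 count and its confidence interval to ocular TEAEs with onset, or increase in severity as in protocol 11.2, during the 56-day treatment period counted from first dose.
- **SAP 2.2:** count the 56 days from first dose. The matching sentence in protocol 5.2.1 and the synopsis can follow at the next amendment.
- **SAP 6.14.1:** keep the last-dose-plus-30-days rule for the other TEAE tables.
- **Follow-up:** tabulate ocular TEAEs with onset on Days 57 to 84 separately, matching the split in 6.14.1.2.
- **Combined Part 1 and Part 2 difference:** label it supplementary, since SAP 2.2 confines the primary outcome to Part 2 and Part 1 is open label and not randomised.

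Two secondary clarifications can go into the same edit: whether last administration in 6.14.1 means the actual or the nominal last dose, and how patients who stop early are counted.

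The cost is a few sentences. Onset dates are recorded under protocol 8.2.1, and dosing dates are already derived under SAP 6.9.2. Counting increases in severity also needs the date of worsening, and the documents do not show how the eCRF records it. The one downside is that follow-up events leave the primary table, but they stay visible in their own table and in the listing.
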